3.2.3 Device Operation

The Instrument is turned ON by depressing the ON/OFF button for four seconds. The instrument first verifies proper operation of the internal electronics and beeps once if no errors are detected. Without a Disposable attached, the Screen displays the "Attach Disposable" message. If the Screen displays an error message, the operator should refer to the Troubleshooting section of this manual. If the battery power is low, which is indicated by a flashing battery icon with a single bar, the Instrument should be turned OFF and the batteries removed and placed in the charging stand. When the Instrument is ready, the Disposable is removed from the packaging immediately before a treatment and attached to the Instrument by means of snap clips on the two sides. The Screen now displays the elapsed time, which is "0", the compression force, and the highest Inner Pad temperature.

After the patient is prepared, the Inner Eyelid Pad is placed adjacent to the region of the palpebral conjunctiva containing the meibomian glands to be treated. Figure 5 illustrates the Inner Pad placement for a lower eyelid and Figure 6 shows Inner Pad placement for an upper eyelid. The orifices of the targeted glands should be visible through the Magnifier. The Outer Eyelid Pad is then moved against the outer surface of the eyelid by depressing the Compression Control on the Instrument. Since the Outer Eyelid Pad opposes the Inner Eyelid Pad, this action applies pressure to the eyelid that

can be varied by the force applied to the Compression Control. This force is displayed on the Screen to provide feedback to the user. If compressing the glands using a gentle pressure (force < 3) does not produce secretions, then the tissue should be warmed to approximately 40 to 42 °C to melt the meibum and facilitate expression. Sliding the heater control switch forward causes the Instrument to energize the LEDs.

[figure not shown]

Figure 5: To treat a lower eyelid, the patient is instructed to look up and the Inner Eyelid Pad is placed in the inferior fornix adjacent to the blocked meibomian glands. The Compression Control is then depressed causing the Outer Eyelid Pad to apply pressure against the outer eyelid.

[figure not shown]

Figure 6: Treatment of an upper lid is illustration. The patient is instructed to look down and the Inner pad is placed in superior fornix adjacent to the blocked meibomian glands. The screen content is automatically re-oriented to remain upright when the Instrument is inverted.

3.3 LipiFlow System

The LipiFlow Thermal Pulsation System is a commercially available device used in the treatment of MGD. It is cleared to be marketed by the United States Food and Drug Administration and will be used as the control device in this study.

3.4 LipiFlow Indications for Use

The LipiFlow Thermal Pulsation System is intended for the application of localized heat and pressure therapy in adult patients with chronic cystic conditions of the eyelids, including meibomian gland dysfunction (MGD), also known as evaporative dry eye or lipid deficiency dry eye.

3.5 LipiFlow Components

The LipiFlow Console provides the user interface and control elements of the system, including all software, algorithms and control elements. The Activator, a single-use sterile device, delivers automated therapeutic energies to each meibomian gland. Its contoured design vaults the cornea and protects the eye allowing a maximum therapeutic temperature of 43 degrees Celsius to reach glands from the inner eyelid, without damaging the eyelid or delicate structures of the globe. Insulation protects the cornea from exceeding a safe 39.5 degrees Celsius, while a pressure feedback loop sends pulsed sequences to expel blockages. Force equalization protects the globe from pressure transmission by focusing energy only on the eyelid. Delivered through the LipiFlow Activator, Vectored Thermal Pulse™ (VTP) technology applies a combination of heat and pressure to the inner eyelid to safely remove gland obstructions and stagnant gland content. Vectored heat and adaptive force equalization targets the pulse, heat, and pressure on the meibomian glands to maximize effectiveness. Therapeutic motion provides proximal-to-distal parastalsis to clear gland contents.

Figure 7: The LipiFlow Console and Activator disposable

4 CLINICAL STUDY DESIGN

4.1 Objective

The objective of this trial is to evaluate the safety and effectiveness of the iLux System for adults with meibomian gland dysfunction (MGD).

4.2 Description of the Study

This study is a randomized, open-label, multisite clinical trial comparing the iLux System to an active control, which will be the LipiFlow® Thermal Pulsation System. The goal of this study is to verify that technological differences between the iLux System and the LipiFlow System do not adversely affect safety and effectiveness. The comparison between the two systems will determine if the iLux System is non-inferior to the LipiFlow System. The proposed sample size is 256 eyes (128 subjects) to demonstrate non-inferiority of treatment with iLux relative to treatment with LipiFlow for the two coprimary effectiveness endpoints. A total of 142 subjects is requested to allow for 10% fallout during patient screening. One hundred twenty-eight subjects will be randomized for bilateral treatment and will be assigned in a 1:1 ratio into the iLux treatment group or the control group at least 7 study sites.

4.3 Non-Significant Risk

The iLux device is a non-significant risk device because it does not meet the criteria for a significant risk device.

The criteria for a significant risk device are as follows¹:

1. The device is intended as an implant and presents a potential for serious risk to the health, safety, or welfare of a subject;
2. The device is purported or represented to be for use supporting or sustaining human life and presents a potential for serious risk to the health, safety, or welfare of a subject;
3. The device is for a use of substantial importance in diagnosing, curing, mitigating, or treating disease, or otherwise preventing impairment of human health and presents a potential for serious risk to the health, safety, or welfare of a subject; or
4. The device otherwise presents a potential for serious risk to the health, safety, or welfare of a subject.

4.4 Outcome Measures

4.4.1 Co-Primary Effectiveness Endpoints

The co-primary effectiveness endpoints are the changes from baseline to the 4-week exam in total Meibomian Gland Score (MGS) and Tear Break-Up Time (TBUT). MGS must be assessed by a masked

¹ "Information Sheet Guidance for IRBs, Clinical Investigators, and Sponsors Significant Risk and Nonsignificant Risk Medical Device Studies", FDA CDRH, January 2006.

rater. Clinical and statistically significant improvements from baseline for each parameter are required to achieve success for these co-primary endpoints.

The MGS is determined for the lower eyelids using a device that applies a standardized pressure to an area including 5 glands (Meibomian Gland Evaluator, Model MGE-1000, TearScience, Inc.) while viewing the eyelid margin using a slit lamp microscope to determine the presence and quality of the gland secretions. A total of 15 glands in three lower eyelid zones (nasal, medial, temporal) will be evaluated. Each gland is graded from 0 to 3 (0 = no secretion, 1 = inspissated, 2 = cloudy, 3 = clear liquid). The maximum MGS score is 45 in each eye. This endpoint has been used in previous studies evaluating the LipiFlow device [5, 6]. The clinician performing the MGS must not be involved in the study procedure and must be blinded to which arm of the study the subject is randomized.

TBUT is evaluated using the fluorescein method [4]. This measurement provides an aggregate assessment of the effectiveness of treatments to both the lower and upper eyelids.

4.4.2 Secondary Effectiveness Endpoint

The secondary effectiveness endpoint will be the change from baseline in patient symptoms using the Ocular Surface Disease Index (OSDI) at the 4-week exam. OSDI is a scoring that evaluates patient symptoms based on a validated questionnaire [7]. This assessment has been used in several clinical studies for treating MGD with the LipiFlow [5, 6].

4.4.3 Primary Safety Endpoint

The primary safety endpoint will be a comparison of the incidence of device-related adverse events (e.g., changes in the lid margin, development of floppy eyelids, entropion or ectropion; and lash integrity) for the two treatments.

4.4.4 Secondary Safety Endpoint

A secondary safety endpoint will be following assessments:

- The evaluation of discomfort and pain during treatment
- Changes from baseline following treatment for the test and control devices for the following assessments:
 - Ocular Surface Staining
 - Intraocular Pressure
 - Best Spectacle Corrected Visual Acuity (BSCVA)

5 PATIENT POPULATION

The study will include adult subjects with symptoms of MGD/evaporative dry eye

5.1 Inclusion Criteria

1. Age 18 years and older of any gender or race.
2. Provision of written informed consent prior to study participation.
3. Willingness and ability to return for all study visits.
4. A positive history of self-reported dry eye symptoms for three months prior to the study using the Ocular Surface Disease Index (OSDI) questionnaire, and a score of ≥ 23 at the baseline visit.

5. Evidence of meibomian gland (MG) obstruction, based on a total Meibomian Gland Score (MGS) of ≤ 12 in the lower eyelids for each eye. A total of 15 glands are evaluated using a standardized pressure device (Meibomian Gland Evaluator, Model MGE-1000, TearScience Inc.) in the nasal, medial, temporal zones of the lower eyelid of each eye (5 glands each zone). Glands expressed and graded from 0 to 3 (0 = no secretion, 1 = inspissated, 2 = cloudy, 3 = clear liquid). The maximum MGS score is 45 for each eye. The rater of MGS must not be involved in the study procedure.
6. Tear break-up time < 10 seconds
7. Agreement/ability to abstain from dry eye/MGD medications for the time between the treatment visit and the final study visit. Ocular lubricants are allowed if no changes are made during the study.

5.2 Exclusion Criteria

1. History of ocular surgery including intraocular, oculo-plastic, corneal or refractive surgery within 1 year
2. Subjects with giant papillary conjunctivitis
3. Subject with punctal plugs or who have had punctal cautery
4. Ocular injury or trauma, chemical burns, or limbal stem cell deficiency within 3 months of the baseline examination
5. Active ocular herpes zoster or simplex of eye or eyelid or a history of these within the last 3 months
6. Subjects who are aphakic
7. Cicatricial lid margin disease identified via slit lamp examination, including pemphigoid, symblepharon, etc.
8. Active ocular infection (e.g., viral, bacterial, mycobacterial, protozoan, or fungal infection of the cornea, conjunctiva, lacrimal gland, lacrimal sac, or eyelids including a hordeolum or sty))
9. Active ocular inflammation or history of chronic, recurrent ocular inflammation within prior 3 months (e.g. retinitis, macular inflammation, choroiditis, uveitis, iritis, scleritis, episcleritis, keratitis)
10. Ocular surface abnormality that may compromise corneal integrity (e.g., prior chemical burn, recurrent corneal erosion, corneal epithelial defect, Grade 3 corneal fluorescein staining, or map dot fingerprint dystrophy)
11. Lid surface abnormalities (e.g., entropion, ectropion, tumor, edema, blepharospasm, lagophthalmos, severe trichiasis, severe ptosis) that affect lid function in either eye
12. Anterior blepharitis (staphylococcal, demodex or seborrheic grade 3 or 4)
13. Systemic disease conditions that cause dry eye (e.g., Stevens- Johnson syndrome, vitamin A deficiency, rheumatoid arthritis, Wegener's granulomatosis, sarcoidosis, leukemia, Riley-Day syndrome, systemic lupus erythematosus, Sjogren's syndrome)
14. Unwillingness to abstain from systemic medications known to cause dryness for the study duration.
15. Women who are pregnant, nursing, or not utilizing adequate birth control measures.
16. Individuals who have either changed the dosing of systemic or non-dry eye/MGD ophthalmic medication within the past 30 days prior to screening
17. Individuals who are unable or unwilling to remain on a stable dosing regimen for the duration of the study.
18. Individuals using isotretinoin (Accutane) within 1 year, cyclosporine-A (Restasis) or lifitegrast ophthalmic solution (Xiidra) within 3 months, or any other dry eye or MGD medications (antibiotics, non-steroidals anti-inflammatory drugs and corticosteroids) for at least 2 weeks and

to maintain abstinence throughout the duration of the study (ocular lubricants are allowed if no changes are made during the study).

19. Individuals wearing contact lenses at any time during the prior three months
20. Individuals that were treated with LipiFlow in one or two eyes in the last 24 months.
21. Eyelid tattoos, including permanent eyeliner makeup
22. Individuals using another ophthalmic investigational device or agent within 30 days of study participation.
23. Individuals who are unable to complete the required patient questionnaires in English.

6 STUDY PROCEDURES

6.1 Subject Enrollment

Patients will be screened, assessed, treated and followed according to the schedule in Appendix A. Patients must have the study explained to them by a member of the site study team, they must be provided sufficient time to consider their participation in the study and provided an opportunity to ask questions of the study team. Subjects must sign the most current version of an informed consent form (ICF) approved by an Institutional Review Board (IRB). All patients who sign an ICF are considered enrolled subjects in the study. Therefore, patients should be screened to the extent possible prior to signing an ICF but patients should not undergo any study-specific assessments until they have signed the ICF.

Enrolled subjects will be assigned a unique study identification (ID) number. No subject-specific information (e.g., initials) will be used in the ID number. Only the study ID number will be used to identify subjects once they are enrolled.

6.2 Subject Withdrawal

Subjects may withdraw their consent to participate in the study at any time, for any reason. Investigators may also withdraw subjects from the study at their discretion in order to protect the rights, safety, or welfare of the subject. All withdrawn subjects will be included in study analyses but they will not be replaced. No missing data will be imputed.

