7 DATA ANALYSIS

Descriptive statistics will be provided to summarize outcomes at each visit as well as for change from baseline. Continuous endpoints will be summarized with N, mean, standard deviation, minimum, maximum, and median. Categorical or binary endpoints will be summarized by count and percentage. Analysis of covariance (ANCOVA) will be used to assess the treatment effect between baseline and 4 weeks for iLux and LipiFlow (LF) treatments for the primary and secondary effectiveness endpoints. For each endpoint analyzed, the baseline value will be used as a covariate.

Given that non-inferiority is demonstrated for the iLux endpoints, success will not be claimed unless the mean change from baseline in the test arm is clinically significant and significantly different from

zero. For any endpoints for which non-inferiority is demonstrated and mean changes from baseline are clinically significant and significantly different from zero, a test for superiority will be performed.

All subjects enrolled and treated in the study shall be included as part of the safety analysis.

Subjects who are randomized but not treated for any reason will be included in the intent-to-treat analysis as part of the arm to which they are randomized but they will be excluded from the per-protocol analysis.

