7.2.4 Sample Size Justification

The proposed sample size is 256 eyes (128 subjects) for this open-label, prospective multicenter trial designed to demonstrate non-inferiority of treatment with iLux relative to treatment with LipiFlow for the primary effectiveness endpoint. A total of 142 subjects is requested to allow for 10% fallout during patient screening. This study design provides a combined power of 88% to demonstrate non-inferiority given the following primary endpoint assumptions:

- MGS non-inferiority delta of 5 points and standard deviation of 8 points, provides a MGS primary endpoint power of 93.9%.
- TBUT non-inferiority delta of 2.5 seconds and standard deviation of 4 seconds, provides a TBUT primary endpoint power of 93.9%
- Power that both endpoints are significant, assuming independence, is $0.939^2 = 0.882$, or 88.2% power.

For the secondary endpoint, a standard deviation of 14 is assumed based on pilot data and the non-inferiority delta is set to 7. The chosen sample size and $\alpha = .025$ provides 80% power for this endpoint.

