7.2.7 Missing Data

Primary and secondary effectiveness endpoints will be imputed when missing to preserve the randomization in the intent-to-treat analysis population. The primary method of imputation used will be by multiple imputation. Ten imputations will be produced for each endpoint using SAS PROC MI. The seed used to begin random number generation will be 11142016. The Markov chain Monte Carlo method will be used to compute with the following predictor variables: baseline tear break-up time, baseline MGS score, gender, and age. Alternate imputation methods used to assess sensitivity to the presence of missing data will be last observation carried forward (LOCF), best case (a test subject's best prior value and a predicate subject's worst prior value is imputed) and worst case (a test subject's worst prior value and a predicate subject's best prior value is imputed). If best case and worst case

conclusions differ, a tipping point analysis will be performed. In the absence of post-treatment data, baseline values will be used for imputation for alternate imputation methods.

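### Section 6.2 forbids imputing missing data and Section 7.2.7 requires it for the effectiveness endpoints; no text says which governs, and what the choice is worth depends on the imputation model

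*Combined protocol and SAP*

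**What the plan says.** Section 6.2 (Subject Withdrawal) states: "All withdrawn subjects will be included in study analyses but they will not be replaced. No missing data will be imputed". The ban is not limited by endpoint, visit or analysis population.

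Section 7.2.7 (Missing Data) states: "Primary and secondary effectiveness endpoints will be imputed when missing to preserve the randomization in the intent-to-treat analysis population". It continues: "The primary method of imputation used will be by multiple imputation". It fixes ten imputations, a seed, the MCMC method and four predictors: baseline tear break-up time (TBUT), baseline MGS, gender and age. It adds LOCF, best-case and worst-case alternates, and a tipping-point analysis if best and worst case disagree. It also covers subjects never seen after treatment: "In the absence of post-treatment data, baseline values will be used for imputation for alternate imputation methods".

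Section 7 (Data Analysis) adds: "Subjects who are randomized but not treated for any reason will be included in the intent-to-treat analysis".

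Neither Section 6.2 nor Section 7.2.7 refers to the other, and no other text gives one precedence.

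**The concern.** For a subject with no Week-4 MGS, TBUT or OSDI value, one section tells the analyst to impute in the intent-to-treat (ITT) population and the other forbids it. Taken literally, Section 6.2 removes the primary missing-data method, all three alternates and the tipping-point analysis that they can trigger. Both co-primary endpoints and the secondary endpoint are affected.

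The trial is open-label. If the rule is settled only after outcome data have accrued, the choice is open to challenge, whichever way it goes. If no Week-4 value is missing, the two rules give the same analysis.

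**Working it through.** **1. The two rules side by side**

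| | Section 6.2 | Section 7.2.7 |
|---|---|---|
| Scope | all missing data | missing primary and secondary effectiveness endpoints, ITT |
| Action | no imputation | multiple imputation, plus LOCF, best case, worst case |
| Effect on a missing Week-4 value | subject drops out of the Week-4 ANCOVA | subject enters with imputed values |

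The scopes overlap on exactly the values that matter, since withdrawn subjects are an obvious source of missing Week-4 data.

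**2. The plan's own power figure**

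Section 7.2.4 says: "The proposed sample size is 256 eyes (128 subjects) for this open-label, prospective multicenter trial", hence 64 per arm at 1:1. It also says: "MGS non-inferiority delta of 5 points and standard deviation of 8 points, provides a MGS primary endpoint power of 93.9" percent. One-sided alpha is taken as 0.025. The plan states that value for the secondary endpoint, and it fits the co-primary figure.

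- Standard error = 8 × √(2/64) = 1.414.
- Noncentrality = 5 / 1.414 = 3.54, with 126 degrees of freedom.
- Noncentral-t power at true difference 0 = 93.9%, as stated. One-sided 0.05 would give 96.9%.

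**3. Missingness has to be assumed**

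The 10% allowance in Section 7.2.4 is for screening fallout, and no loss rate after randomization is given. Assumed here: 5%, 10% and 20% (6, 13 and 26 of 128), completely at random, with baseline and the other predictors unrelated to outcome. Analytic complete-case power for MGS is then 92.8%, 91.3% and 87.8%.

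**4. Complete-case versus imputation with arm in the model**

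Simulated MGS claim rates: 10,000 trials per cell, ANCOVA on baseline, ten imputations, Rubin's rules, Monte Carlo standard error at most 0.5 points.

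| True difference | 5% missing | 10% missing | 20% missing |
|---|---|---|---|
| 0 | 92.5 vs 92.1% | 91.1 vs 90.6% | 87.3 vs 85.5% |
| −1 | 77.8 vs 77.4% | 75.2 vs 74.6% | 70.0 vs 67.6% |
| −2 | 53.5 vs 53.2% | 51.4 vs 50.3% | 46.5 vs 43.9% |

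The gaps run from 0.3 points (53.5 − 53.2) to 2.6 points (46.5 − 43.9), with complete-case higher in every cell.

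**5. Complete-case versus imputation with the predictors as listed**

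Arm is not among the four predictors. Imputed values then come from one distribution for both arms and carry no treatment difference, so the expected estimate shrinks from Δ to Δ × (1 − fraction missing). With 26 of 128 missing, −2 becomes −2 × 102/128 = −1.59, and a true difference at the margin becomes −5 × 102/128 = −3.98.

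Simulated claim rates, complete-case versus imputed without arm:

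| True difference, missing | 2,000 trials per cell | 4,000 trials per cell |
|---|---|---|
| −2, 10% | 52.0 vs 57.2% | 51.6 vs 57.0% |
| −2, 20% | 46.3 vs 58.1% | 45.4 vs 57.4% |
| −5 (margin), 10% | not run | 2.4 vs 3.6% |
| −5 (margin), 20% | 3.0 vs 5.2% | 2.5 vs 5.5% |

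The largest Monte Carlo standard error is √(0.5 × 0.5/2,000) = 1.1 points in the first run and 0.8 in the second. A further run of 3,000 trials per cell, with baseline as the only predictor, gave 52.7 vs 55.2%, 49.4 vs 55.4% and 44.9 vs 57.2% at −2 for 5%, 10% and 20% missing.

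At −2, the complete-case and no-arm verdicts differ in 6.4% of trials at 10% missing, and in 12.3% to 12.7% at 20%.

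**The case against.** The strongest reply is that nobody would be misled. Section 7.2.7 carries the title for this topic, sits in the analysis chapter and is specified down to the seed; Section 6.2 is procedural. A statistician would very probably follow Section 7.2.7. That stands as a view of intent, but the documents do not say it. Confining Section 6.2 to safety or per-protocol data would also resolve the conflict, but its wording has no such limit.

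A reader might infer that Section 6.2 also contradicts its own promise to include withdrawn subjects, and the ITT inclusion statement in Section 7. The documents do not support that. Withdrawn subjects can enter descriptive and safety summaries without imputation. Only a subject with no Week-4 value is affected, and only in the Week-4 ANCOVA. The inclusion statements favour Section 7.2.7 as the intended rule; they are not further contradictions.

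A reader might also infer that the choice of rule is immaterial. That holds approximately if arm is in the model or imputation is run by arm. The plan neither states nor forbids either, and with the listed predictors alone it does not hold.

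**Conclusion.** The contradiction is real and should be resolved before database lock. It leaves the handling of a missing co-primary value unsettled, although Section 7.2.7 is probably what was meant.

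The effect is conditional. Under 5–20% missing completely at random, complete-case and imputed MGS claim rates differ by about 0–3 points with arm in the imputation model. With the predictors as listed, imputation favours a non-inferiority claim when the test device is truly worse: at −2, by about 5 points at 10% missing and 12 points at 20%. At the margin with 20% missing, the false-claim rate is about 5% against a nominal 2.5%.

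The loss rates, the mechanism and the nonzero true differences are assumptions. These are also single-endpoint rates. It would be wrong to read them as changes in overall trial success, which also requires TBUT and the change-from-baseline criteria.

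**What to change.** - In Section 6.2, delete the no-imputation sentence, or limit it to data other than the primary and secondary effectiveness endpoints. Cross-refer to Section 7.2.7 as the governing rule for ITT effectiveness analyses.
- In Section 7.2.7, state that imputation is done separately by treatment arm or with arm in the model. Naming this section as governing without that statement would leave the shrinkage shown above in place.
- Optionally, keep a complete-case ANCOVA as a labelled sensitivity analysis.

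The cost is a few sentences, with no change to data collection or sample size.
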